We hope to determine how regular cannabis use alters resting brain activity in people with MS.

c) **Proposed Start Date (may not precede IRB approval date):**

August 2016

2.

Study Procedures (If this is a student project, the methods section of the thesis or dissertation proposal must be attached in section #16 - Attachment section.)

a) **In lay language, describe all the procedures, from screening through end-of-study, that the human subject must undergo in the research project, including study visits, drug treatments, randomization and the procedures that are part of standard of care. Please note: Do NOT respond "See Attachment Section." If you would like to add tables, charts, etc., attach those files in the Attachment section (#16).**

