**\*\*\* Subject Population (a-g) \*\*\***

8.

Subject Population - In the space below, please detail the participants that you are requesting to recruit (include requested participant number and description of each group requested). (Input N/A if not applicable)

- a) **Requested Participant Description (Include number of participants that you plan to study and description of each group requested, if applicable).**

We plan on recruiting 40 people with MS: 20 are regular cannabis users (smokers), 20 are not users, with an estimate that approximately 5 from each group will not complete the study (i.e. drop out).

- b) **What is the rationale for studying the requested group(s) of participants?**

To investigate the effects of medical marijuana usage on physical function we will employ an observational case-control design. Cases (MS medical marijuana users) will be compared to age, sex, and disease duration matched controls (MS non-cannabis users). The research team has experience with all the methods involved.

- c) **If applicable, state the rationale for involvement of potentially vulnerable subjects to be entered into the study, including minors, pregnant women, economically and educationally disadvantaged, or decisionally impaired subjects. Specify the measures being taken to minimize the risks and the chance of harm to the potentially vulnerable subjects.**

N/A

- d) **If women, minorities, or minors are not included, a clear compelling rationale must be provided. Examples for not including minors: disease does not occur in children; drug or device would interfere with normal growth and development; etc.**

N/A

- e) **State if any of the subjects are students, employees, or laboratory personnel. They should be presented with the same written informed consent. If compensation is allowed, they should also receive it.**

N/A

- f) **Describe how potential subjects will be identified for recruitment (e.g., chart review, referral from individual's treating physician, those individuals answering an ad). How will potential participants learn about the research and how will they be recruited (e.g., flyer, email, web posting, telephone, etc.)? Attach recruitment materials in the Attachment Section (#16). Important to remember: potential subjects may not be contacted before IRB approval.**

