### *Statistical Analysis*

All data are reported as Mean (Standard Deviation) unless otherwise noted. Pearson's correlations were calculated between demographic variables (age, height, weight, BMI, disease duration) and whole brain SUV to identify possible covariates for the SPM analysis. Significant factors were individually tested as covariates during SPM analysis.

Demographic, clinical, and extracted regional SUV variables were compared between the two groups using unpaired student's t-tests. If a clinical variable differed between the two groups a Pearson's correlation was performed with it and regional SUVs. Cohen's D measures of effect size were calculated for the regional SUVs. Analysis was performed using IBM SPSS Statistics for Windows version 24 (IBM Corp., NY, USA) with alpha set to 0.05.

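### The regional SUV t-tests and the follow-up clinical-by-region correlations are all run at a per-test 0.05, with no multiplicity control and no exploratory label.

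*Combined protocol and SAP*

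**What the plan says.** The imaging aim is in the Purpose section, item 1(b): "We hope to determine how regular cannabis use alters resting brain activity in people with MS". It names no region and no criterion for deciding that brain activity is altered.

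The Statistical Analysis section gives two layers of SPSS tests on the regional values.

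- Layer 1: "Demographic, clinical, and extracted regional SUV variables were compared between the two groups using unpaired student's t-tests".
- Layer 2: "If a clinical variable differed between the two groups a Pearson's correlation was performed with it and regional SUVs".

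One significance level covers both: "with alpha set to 0.05". Effect sizes are also planned: "Cohen's D measures of effect size were calculated for the regional SUVs".

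The same section describes an SPM analysis, with covariates screened by correlation with whole-brain SUV: "Significant factors were individually tested as covariates during SPM analysis". It gives no SPM threshold, no correction within SPM, no list or number of regions, and no account of how the regions were extracted. No other section of the protocol addresses multiplicity.

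**The concern.** Regions are plural in both layers, so the imaging question gets several chances to produce p<0.05. Each clinical variable that differs between groups adds a further row of tests across all regions. With no primary region, correction or exploratory label, a reader cannot tell an isolated p=0.03 among many regions from a result that holds up across the whole set.

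The two layers can also reinforce each other. A chance regional difference may be followed by a chance correlation with a motor or symptom score, and the pair then looks like a functional explanation.

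Naming a motor primary outcome would leave the imaging tests as they are. Fixing several regions in advance would not be enough either, since several fixed regions still give several chances.

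**Working it through.** **Inputs from the documents**

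- Per-test alpha 0.05 (Statistical Analysis).
- Group size: "We plan on recruiting 40 people with MS: 20 are regular cannabis users (smokers), 20 are not users", with about 5 per group expected not to complete (Subject Population, item 8(a)). That gives 15 to 20 per group.

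**Inputs that must be assumed**

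- Number of regions m: 2 to 10, fixed independently of the group comparison.
- Correlation between regions: 0.5 to 0.9.
- Number of flagged clinical variables q.
- Two-sided tests, and that the scanned group is as large as the recruited group.

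The plan states no family-wise rate, so there is no figure of its own to reproduce. With m = 1 the rate is 0.05, which only checks the formula.

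**Step 1: independent regions, t-tests only (an upper reference)**

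P(at least one false positive) = 1 − 0.95^m.

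- m = 2: 1 − 0.9025 = 0.0975
- m = 6: 0.265
- m = 10: 0.401

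**Step 2: correlated regions, t-tests only**

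Simulation under no group difference with equally correlated normal values. The results at 15 and at 20 per group are nearly the same.

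| Regions | correlation 0.5 | 0.8 | 0.9 |
|---|---|---|---|
| 2 | 9% | 8% | 7% |
| 4 | 16% | 12% | 9% |
| 6 | 21% | 14% | 11% |
| 10 | 29% | 17–18% | 13% |

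As multiples of the per-test alpha: 7/5 = 1.4 at the low end and 29/5 = 5.8, about 6, at the high end.

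**Step 3: the correlation grid, given that variables have been flagged**

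Settings: 6 regions, 15 per group, flagged variables correlated at 0.5 with each other and unrelated to the regions. Chance of at least one false correlation:

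- one flagged variable: 14% (region correlation 0.8) to 21% (0.5)
- two: 24% to 35%
- three: 32% to 47%

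These rates apply only after the flagging has happened.

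**Step 4: both layers together, not conditional on flagging**

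Settings: 15 clinical variables assumed, correlated at 0.3, with no true difference anywhere. Chance of any false t-test or any triggered false correlation:

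- 2 regions, correlation 0.9: 11% to 12%
- 5 regions, correlation 0.8: 20%
- 10 regions, correlation 0.5: 41%

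**Step 5: what correction costs**

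Power comes from the noncentral t with d = 1.0 and noncentrality √(n/2). The strictest Holm step for 6 regions is 0.05/6 = 0.0083.

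- 15 per group (noncentrality 2.74, 28 df): 75% at 0.05 and 47% at 0.0083.
- 20 per group (noncentrality 3.16, 38 df): 87% at 0.05 and 65% at 0.0083.

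**The case against.** The strongest objection concerns the SPM step. It is mentioned before the extracted-region tests, and its threshold is not given. If the regions were cut out of SPM group-difference clusters, the difficulty is circular selection. The rates in Step 2 would then not describe it, and Holm over the selected regions would not control it. If SPM was itself corrected, some control already exists for the group comparison. This stands, and it makes the first part of the fix conditional. It does not rescue the clinical-by-region correlations, which a correction of the SPM group comparison does not cover.

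Second, no single multiplier follows from the documents. A reader might infer that false regional claims are a fixed 2 to 6 times as likely as the plan states. The documents do not support that: they give no number of regions and no correlation, and the plan states a per-test alpha, not a family rate. Two highly correlated regions give about 1.4 times 0.05, while more regions or the added grid give more than 6 times.

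Third, the plan has no rule that one significant region or correlation meets the brain aim. A reader might take it that way because nothing excludes it, but no such criterion is written.

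Fourth, the correlations run only if a clinical variable differs. This is correct, and the 24% to 47% must be read as conditional. The trigger is not remote, however. Item 2(a) lists about 16 instruments. If each gave one independent null variable, at least one would be flagged with probability 1 − 0.95^16 = 56%, and less often if they are correlated.

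Fifth, this is a small observational study, the session descriptions contain no scan, and the group sizes used here are those of the motor study. That limits precision, but 15 and 20 per group give nearly the same rates. Small and preliminary work can reasonably be left unadjusted if it is labelled exploratory, and no such label is given.

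**Conclusion.** The concern holds for the SPSS tests. Regional t-tests and clinical-by-region correlations are each run at 0.05 with no multiplicity control or exploratory label, so with two or more regions the chance of at least one false regional result exceeds 5%.

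The size rests on assumptions. For 2 to 10 anatomically fixed regions with correlation 0.5 to 0.9 and 15 to 20 per group, the t-tests alone give about 7% to 29%. The grid adds to this, by an amount that depends on how many variables are flagged.

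A reader might also infer that the SPM analysis was uncorrected. The documents do not show this; they are silent on the SPM threshold. The consequence is for the interpretation of the imaging results, and it can be put right with data already collected.

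**What to change.** In the Statistical Analysis section, state how many regions were tested and how they were defined, then replace the flat 0.05 for the imaging results as follows.

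1. **Regional differences.** If the regions were fixed independently of the group comparison, report Holm or max-T permutation adjusted p-values across all extracted regions, and claim a regional difference only on the adjusted value. If they were extracted from SPM group-difference clusters, base the claim on the multiplicity-corrected SPM result, and present the extracted SUV t-tests and Cohen's d as descriptive only.
2. **Correlation grid.** In either case, report Benjamini-Hochberg q-values across every clinical-variable by region cell, state the number of cells tested, and label the grid exploratory.
3. **Reporting.** Give all tested regions with 95% confidence intervals, significant or not, alongside the effect sizes already planned.

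This takes revised wording and a short re-analysis, with no new participants or procedures. The price is power for any single region, as shown in Step 5: with 6 regions, 15 per group and d = 1.0 it falls from 75% to 47% at the strictest Holm step. Max-T loses less because it uses the correlation between regions.
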